#### 6.3.1 Evaluable for toxicity

Patients evaluable for safety/toxicity: Any patient receiving study treatment during the DLT eval period- start of nivolumab C1D15 to end of cycle 3. Therefore, any patients who do not receive nivolumab will not be evaluable for safety and will be replaced.

### 6.3.2 Evaluable for response

Patients evaluable for response: Any patient who receives all of the 3 study drugs. These patients will not be replaced.

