1 out of 3	
Enter 3 more subjects at this dose level.
 
 
• If 0 of these 3 subjects experience DLT, proceed to the next dose level.
 
• If 1 or more of this group suffer DLT, then dose escalation is stopped, and this dose is declared the maximally administered dose. Three (3) additional subjects will be entered at the next lowest dose level if only 3 subjects were treated previously at that dose.
 

$\geq 2$	Dose escalation will be stopped. This dose level will be declared the maximally administered dose (highest dose administered). Three (3) additional subjects will be entered at the next lowest dose level if only 3 subjects were treated previously at that dose.
$\leq 1$ out of 6 at highest dose level below the maximally administered dose	This is generally the recommended maximally tolerated dose. At least 6 subjects should be entered at the recommended phase 2 dose.

We expect to enroll a minimum of 6 patients (6 patients treated at DL 1 with 1 or less patient experience DLT) and a maximum of 18 patients (6 at each of the DL 1, -1 and -2) for dose finding part. Once the MTD is determined, patients will be accrued to the expansion cohort to be treated at MTD. Including 6 patients treated at MTD from the dose escalation part, we plan to accrual additional 24 R/R AML patients to the expansion cohort. A total of 30 patients will be treated at MTD to decide whether the response rate (CR rate), P, is less than or equal to 30% (combination drug not of interest) or greater than or equal to 50% (combination drug is promising). If the number of responses out of 30 patients is 13 or more, the hypothesis that  $P \leq 30\%$  is rejected with a target error rate of 0.10 and an actual error rate of 0.084. If the number of

responses is 12 or less, the hypothesis that  $P \geq 50\%$  is rejected with a target error rate of 0.20 and an actual error rate of 0.181.

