To estimate the response rate, defined by CR/Cri, which will be assessed by bone marrow biopsy after cycle 1, cycle 2, cycle 3, then every 3 cycles after this, and at time of relapse. Since this will study will only have a small sample size, it will not be powered to determine an accurate response rate for nivolumab in combination with venetoclax and decitabine. We will plan to estimate response rate, as defined by CR/CRI in all evaluable patients in this study, regardless of dose level of venetoclax, and will not attempt to evaluate response rate for individual dose levels. The response rate along with an exact 95% confidence interval will be reported. However, we can consider our study's response rate in context of recent retrospective studies evaluating venetoclax in combination with HMA as well as the historical response rate with high dose cytarabine-containing regimens where the CR rate is 30-40%. Therefore, a response rate of 50% would be considered promising.

Toxicity will be graded and reported according to the revised NCI Common Terminology Criteria for Adverse Events (CTCAE) version 5.0. All patients who receive any amount of the study drug (Nivolumab) will be evaluable for toxicity.

Dosing schema and dosing alterations can be found in [Section 6.1](#) and [Section 7](#).

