## 9.2 Sample Size/Accrual Rate

The maximum total of 42 patients will be accrued. With the estimated accrual rate of 2-3 patients per month, the maximum accrual time including DLT observation period will be around 18-24 months.

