### 9.3 Analysis of Secondary Endpoints

Every report of our secondary objectives (listed above in Section 1.2) will contain all patients included in the study. For the response calculation, the report will contain at least a section with all eligible patients. Another section of the report may detail the response rate for evaluable patients only. However, a response rate analysis based on a subset of patients will explain which patients were excluded and for which reasons. 95% confidence limits will be given.

Data that are collected serially over time will be explored graphically using box plots and/or individual time plots as well as analytically with either repeated measures analysis of variance or Friedman's nonparametric test. This trial will form the basis for a follow up proposal to examine this combination in a phase 1 study in newly diagnosed AML patients with *TP53* mutations.

We will assess MRD by measuring the mutational burden with variant allele frequency, cytogenetics, and flow cytometry before and after response is achieved to see if there is a change in any of these MRD assessment parameters. We will compare these three MRD tests at the same time points to characterize the importance of different MRD tests in different molecular subsets of AML. We will also evaluate MRD status at each time point in relation to disease outcome using chi square test of independence. This will allow us to determine which MRD assessment(s) performed at which timepoint(s) is most meaningful and helpful in determining relapsed/refractory AML outcomes. For T-Cell response and DNA methylation studies, analyses

of the data will be primarily descriptive in nature given the relatively small sample size.

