### **Treatment Failure (TF)**

Treatment failure will be classified as one of the following:

- 12.1.27** Resistant disease: Failure to achieve a complete remission (CR, CRc, or CRi) or partial remission. Patients who survive  $\geq 7$  days following completion of initial treatment, with evidence of persistent leukemia by blood and/or bone marrow examination.
- 12.1.28** Death in Aplasia: Patients who survive  $\geq 7$  days following completion of initial treatment, but die while cytopenic, with an aplastic or hypoplastic marrow obtained within 7 days of death, without evidence of persistent leukemia

**12.1.29** Death from Indeterminate cause: Patients who die before completion of treatment or < 7 days following completion of initial treatment; patients who die  $\geq$  7 days following completion of initial treatment with no peripheral blood blasts, but no bone marrow examination is available; patients who fail to complete the first cycle of therapy

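### The Section 9.1 response rate leaves out patients lost before nivolumab starts on Day 15, and the 13-of-30 rule does not say which set of patients decides it

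*Combined protocol and SAP*

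**What the plan says.** Five places bear on who is counted.

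- Section 6.3.2: "Patients evaluable for response: Any patient who receives all of the 3 study drugs. These patients will not be replaced". The Schema, Section 6.1 and the study calendar put the first nivolumab dose on Day 15 of cycle 1.
- Section 9.1, decision rule: "A total of 30 patients will be treated at MTD to decide whether the response rate (CR rate), P" is at most 30% or at least 50%. Thirteen or more responses reject the 30% hypothesis. The 30 are built as follows: "Including 6 patients treated at MTD from the dose escalation part, we plan to accrual additional 24 R/R AML patients to the expansion cohort". No evaluability definition is cited.
- Section 9.1, estimation: "We will plan to estimate response rate, as defined by CR/CRI in all evaluable patients in this study, regardless of dose level of venetoclax". An exact 95% confidence interval goes with this rate.
- Section 9.3: "For the response calculation, the report will contain at least a section with all eligible patients". An evaluable-only section is optional, and "However, a response rate analysis based on a subset of patients will explain which patients were excluded and for which reasons".
- Section 12.1.29, under Treatment Failure, includes deaths before completion of treatment and "patients who fail to complete the first cycle of therapy".

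Sections 6.3.1 and 9.1 also replace patients who never receive nivolumab or who leave the DLT window for reasons other than DLT.

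**The concern.** Take a patient who starts decitabine and venetoclax at the MTD level and dies on Day 10. Under 6.3.2 this patient is not evaluable for response and so drops out of the rate in 9.1. Under 9.3 the same patient, if eligible, belongs in the required response section. Under 12.1.29 the same patient is a treatment failure. The 13-of-30 rule does not settle the matter, because being treated at the MTD could mean having received any study drug or all three.

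The exclusion is not neutral. Early deaths and progressions are mostly non-responders, so removing them raises the observed rate. What is at stake is which rate decides whether the combination is called promising. If the choice is left until response data are in hand, it may be made with knowledge of the result.

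The replacement rules add a related gap. They read naturally as serving DLT evaluation, but no sentence says whether a patient lost before Day 15 and replaced in dose finding still counts towards the 30.

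**Working it through.** **Inputs.** From Section 9.1: n = 30, cutoff 13, null rate 0.30, alternative 0.50, target errors 0.10 and 0.20. The documents do not give the share f lost before nivolumab, so f = 3.6% and 5% are assumptions. The 3.6% is the 30-day mortality of the 10-day decitabine plus venetoclax study described in Section 2.4.1. It is only a rough proxy, since it covers deaths alone and a longer window. The response rate q among early leavers is also assumed, at 0% or 15%.

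**1. The plan's own figures.** P(X ≥ 13 | 30, 0.30) = 0.0845 and P(X ≤ 12 | 30, 0.50) = 0.1808. These reproduce the stated 0.084 and 0.181.

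**2. Effect on the reported rate.** Suppose 13 respond, three leave before Day 15, and the three are replaced.
- Three-drug set: 13/30 = 43.3% (exact 95% CI 25.5 to 62.6).
- All starters: 13/33 = 39.4% (22.9 to 57.9).
- Difference: 3.9 percentage points.

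**3. False-go rate if leavers are replaced until 30 patients have had all three drugs, with the 30% null on all starters.** The null rate among three-drug patients becomes p = (0.30 − q·f)/(1 − f), and the false-go rate is P(X ≥ 13 | 30, p).

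| f (assumed) | q | p | False-go rate |
|---|---|---|---|
| 3.6% | 15% | 0.2946/0.964 = 0.3056 | 0.096 |
| 3.6% | 0% | 0.30/0.964 = 0.3112 | 0.108 |
| 5% | 15% | 0.2925/0.95 = 0.3079 | 0.101 |
| 5% | 0% | 0.30/0.95 = 0.3158 | 0.119 |

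The 0.10 target is crossed at f = 4.8% (q = 15%) or f = 2.5% (q = 0%).

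**4. Thirty starters, no replacement, 13 responses still required.** Leavers are non-responders among the same 30, so the error stays at 0.084.

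**5. Could 12 responses pass on the smaller denominator?** Take 30 starters with no replacement, and recompute the cutoff to keep the error at or below 0.10.

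| Losses | n | Error at cutoff 12 | Error at cutoff 13 | Cutoff needed |
|---|---|---|---|---|
| 1 | 29 | 0.129 | 0.065 | 13 |
| 2 | 28 | 0.103 | 0.049 | 13 |
| 3 | 27 | 0.080 | 0.036 | 12 |

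With one or two losses, 12 responses fail on either denominator. With three, 12/27 would pass although 12/30 fails. That requires a recomputed cutoff which the plan does not offer, and its type II error, P(X ≤ 11 | 27, 0.50) = 0.221, exceeds the 0.20 target.

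**6. Power on all starters if 50% is meant only for three-drug patients.** P(X ≥ 13 | 30, 0.50(1 − f)) is 0.819 at f = 0, 0.762 at 3.6% (p = 0.482) and 0.738 at 5% (p = 0.475).

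**The case against.** The strongest reply is that the plan already has most of a hierarchy. Response is a secondary objective and Section 9.3 governs secondary endpoints. There the all-eligible section is mandatory, the evaluable-only section is optional, and exclusions must be explained. This stands to a large extent: a reader might infer that early leavers disappear from the report, and 9.3 rules that out. It does not settle which rate decides the rule, and 9.1 attaches its estimate and interval to the evaluable set.

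It can also be said that 12.1.29 is a response category, not a denominator rule. That is right. It gives these patients an outcome, which makes leaving them out harder to justify, but it does not by itself put them in the denominator.

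The stakes are limited as well. The primary objective is safety and the MTD, and 9.1 itself says the study is too small for an accurate response rate. This bears on size, not on whether the gap exists.

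Three stronger readings are tempting, and the documents do not support them.

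- **The stated errors are wrong.** They are correct for 30 patients. Inflation needs both conditions of step 3, and the natural reading of the replacement rules, for DLT evaluation only, argues against the first.
- **The accrual cap leaves no room for replacements.** Section 9.2 says "The maximum total of 42 patients will be accrued", and 18 + 24 = 42, but 18 is reached only if all three dose levels fill. If dose level 1 is the MTD with six patients, 6 + 24 = 30 and 12 places remain.
- **Replaced patients push the rule past 30.** Section 9.1 fixes the total at 30, and under 6.3.2 a patient who received all three drugs stays response-evaluable even if replaced for DLT purposes. Only patients lost before nivolumab are unresolved.

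**Conclusion.** The point holds in a limited form. Followed as written, 6.3.2 and 9.1 give a response rate that omits losses on Days 1 to 14 and is biased upward. Section 9.3 and 12.1.29 point the other way, and nothing says which set decides the 13-of-30 rule.

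The size is modest: about four percentage points in the illustration with three early losses. The false-go rate moves from 0.084 to roughly 0.10 to 0.12 only under replacement to fill 30 three-drug patients together with an all-starter null. Without replacement it does not move. A reversed decision needs three losses and a cutoff that the plan does not contain.

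All loss rates, and the response rates of early leavers, are assumptions. The direction of the bias rests on early leavers responding less often than patients who reach Day 15, which is hard to doubt when leaving means death or progression.

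**What to change.** Before response data are reviewed, make these changes in 6.3.2 and 9.1.

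1. State that the 13-of-30 rule, and the MTD response rate with its exact interval, use the 30 eligible patients who start cycle 1 Day 1 at the MTD dose level. Anyone who leaves before a response assessment is a non-responder. This set is slightly narrower than the all-eligible set in 9.3, because Section 4.4 allows for registered patients who never start.
2. State that the 30% and 50% rates refer to that set. The stated 0.084 and 0.181 then stand unchanged.
3. State that replacement under 6.3.1 and 9.1 is for DLT evaluation only, and that replaced patients who started at the MTD level still count towards the 30. Set the expansion number at 30 minus those already started at that level, instead of a fixed 24.
4. Report the three-drug rate and the pooled all-dose-level rate as supportive.

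The cost is wording and one supportive table. The observed rate will be slightly lower, and a few of the 30 may never have received nivolumab. If the sponsor means 50% only for patients who receive all three drugs, power falls from 0.819 to 0.762 at 3.6% loss or 0.738 at 5%, both loss rates assumed, and the plan should say so.

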### 6.3.3 Progressive disease stopping rule

Stopping rule: if >50% of patients have disease progression prior to finishing cycle 3, the study PI and sponsor will consider stopping the study due to ineffective treatment.

## 6.4 General Concomitant Medication and Supportive Care Guidelines

Do not administer live attenuated vaccines prior to, during, or after treatment until B-cell recovery occurs.

### 6.4.1 Concomitant Medications with Venetoclax

Venetoclax is predominantly metabolized by CYP3A4/5. Concomitant use of venetoclax with strong inhibitors of CYP3A at initiation and during ramp-up phase is contraindicated. For patients who have completed the ramp-up phase and are on a steady daily dose, reduce the dose by at least 75% when used concomitantly with strong CYP3A inhibitors. Resume the venetoclax dose that was used prior to initiating the CYP3A inhibitor 2 to 3 days after discontinuation of the inhibitor.

Avoid concomitant use of moderate CYP3A inhibitors or P-gp inhibitors. If a moderate CYP3A inhibitor or a P-gp inhibitor must be used, reduce the dose by at least 50%. Resume the dose that was used prior to initiating the CYP3A inhibitor or P-gp inhibitor 2 to 3 days after discontinuation of the inhibitor. If a narrow therapeutic index P-gp substrate must be used, it should be taken at least 6 hours before venetoclax.

Avoid concomitant use with strong CYP3A inducers or moderate CYP3A inducers.

Venetoclax may cause a significant increase in Cmax and AUC of warfarin. International normalized ratio (INR) should be monitored closely in patients receiving warfarin.

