#### 2.5.4 Pharmacokinetic (PK) and Pharmacodynamic (PD) studies

While the combination of decitabine and venetoclax has been studied and is currently being utilized clinically, adding nivolumab to this combination is novel. Venetoclax has low bioavailability, high inter-patient PK variability, and is susceptibility to drug-drug interactions (DDIs) through inhibition of intestinal CYP3A4, P-glycoprotein (P-gp), and BCRP and liver CYP3A4 and OATP1B1. Antifungal agents, which are routinely administered concurrently with venetoclax, are moderate-to-strong inhibitors of CYP3A4, and the drug transporters P-gp, BCRP, and OATP1B1. The unpredictable PK properties of venetoclax and high DDI potential warrant detailed plasma PK evaluation of venetoclax during AML therapy.

Plasma biomarker assays for OATP1B1 activity will also be incorporated to determine

OATP1B1 activity in relation to antifungal and venetoclax treatment (DOI: 10.1124/dmd.119.089474). As liver uptake by the transporters OATP1B1 can be a rate-limiting step to CYP3A4-mediated drug metabolism, and azoles and echinocandins are potent inhibitors of OATP1B1, we will also measure plasma biomarkers for OATP1B1 activity before and after administration antifungal/venetoclax. In order to assess the degree of OATP1B1 inhibition, analysis of glycochenodeoxycholate sulfate (GCDGA-S) and chenodeoxycholate-24-glucuronide (CDCA-24G) levels will be performed in plasma samples as validated surrogate endogenous substrates of OATP1B1/OATP1B3. Previous clinical studies have indicated that the AUC of GCDCA-S can be increased >20-fold following treatment with OATP1B1/3 inhibitors, whereas CDCA-24G is only detectable after the administration of OATP1B1/3 inhibitors. In addition to these bile acids, the co-proporphyrins CP-I and CP-III will be examined as OATP1B1/3 biomarkers. These compounds are known OATP1B1/3 substrates in vitro, and their plasma levels are significantly increased in Oatp1a/1b gene cluster knockout mice, compared with wild-type animals (up to 18.4-fold) as well as in humans receiving OATP1B1/3 inhibitors. The selectivity of CP-I and CP-III for OATP1B1 and OATP1B3 has been confirmed by the demonstration that these compounds are not transported by OCT1, OCT2, OAT3, or NTCP.

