#### 6.4.1.1 Venetoclax Dose Adjustments with Common Antifungals and Other CYP3A Inhibitors

The dose of venetoclax should be adjusted to the following doses if taken with these antifungal medications:

Posaconazole:

Ramp-up Day 1- 20 mg venetoclax

Ramp-up Day 2- 50 mg venetoclax

Day 3 and onward- 70 mg venetoclax

Moderate CYP3A Inhibitors (ex. Fluconazole/Isavuconazole):

Ramp-up Day 1- 50 mg venetoclax

Ramp-up Day 2- 100 mg venetoclax

Day 3 and onward- 200 mg venetoclax

Strong CYP3A Inhibitors (ex. Voriconazole):

Ramp-up Day 1- 20 mg venetoclax

Ramp-up Day 2- 50 mg venetoclax  
Day 3 and onward- 100 mg venetoclax

Because there is a potential for interaction of nivolumab, decitabine, and venetoclax with other concomitantly administered drugs, the case report form must capture the concurrent use of all other drugs, over-the-counter medications, or alternative therapies. The Principal Investigator should be alerted if the patient is taking any agent known to affect or with the potential for drug interactions. The study team should check a frequently-updated medical reference for a list of drugs to avoid or minimize use of. Appendix D (Patient Drug Interactions Handout and Wallet Card) should be provided to patients if available.

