Plasma venetoclax and serum nivolumab concentration-time profiles will be analyzed by non compartmental analysis in Phoenix Winonlin, and subsequently by population mixed effects PK modeling using NONMEM. Pharmacokinetic parameters (e.g., Cmax, AUC, CL, V, and t1/2) will be estimated. For venetoclax PK, concurrent antifungal medications will be grouped as strong (e.g., posaconazole, voriconazole) or moderate (e.g., fluconazole, isavuconazole) CYP3A4 inhibitors, or OATP1B1 inhibitors (e.g, micagungin) and included as a covariate in the venetoclax population PK model. Associations between: 1) antifungal drug administered and/or venetoclax exposure and changes in OATP1B1 plasma biomarkers from baseline to post-treatment; and 2) drug exposure parameters such as Cmax and AUC with toxicity or response will be performed using standard t-tests or Wilcoxon rank sum tests and illustrated using boxplots or other graphical displays. Values will be log transformed as appropriate to reflect biologic plausibility assessment.

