## 11. STUDY CALENDAR

Baseline evaluations are to be conducted within 10 days prior to start of protocol therapy. In the event that the patient's condition is deteriorating, laboratory evaluations should be repeated within 48 hours prior to initiation of the next cycle of therapy.

	Pre-Study	Induction cycle 1	Induction cycles 2-3 (If needed)	Maintenance cycles	Relapse/Off Study
Decitabine		D	D	D	
Nivolumab		N	N	N	
Venetoclax		V	V	V	
Informed consent	X				
Demographics	X				
Medical history	X				
Concurrent meds a	X	X	X	X	
Physical exam b	X	X	X	X	X
Vital signs c	X	X			X
Height	X				
Weight	X	X			X
Performance status d	X	X			X
Serum Chemistry e	X	X	X	X	X
CBC w/diff f	X	X	X	X	X
EKG	X				
Adverse event evaluation g	X	X	X	X	X
Pregnancy test h	X	X	X	X	
Bone marrow i	X	X	X	X	X
Correlative studies j	X	X	X	X	X

D: Decitabine will be given on Days 1-10 of Induction cycles and Days 1-5 of maintenance cycles

N: Nivolumab will be given on Day 15 of cycle 1 and Days 1 and 15 of all subsequent cycles

V: Venetoclax will be given on Days 1-28 of induction cycles and Days 1-21 of maintenance cycles. Dosing ramp-up on days 1-3 or 1-4 (based on concurrent use of CYP3A inhibitors as outlined in Section 6.3.1)

a: Concurrent medications should be assessed at screening and the beginning of each treatment cycle

b: Physical exam should be performed at Screening, Days 1 and 15 of every cycle and End of Treatment/Relapse

c: Vital signs should be performed at Screening, Days 1 and 15 of every cycle and End of Treatment/Relapse. Vitals signs include blood pressure, heart rate, temperature, oxygen saturation, and respiratory rate.

d: Performance status should be evaluated at Screening, Day 1 of each cycle of therapy, and End of Treatment/Relapse

e: Serum chemistry will include: Na, K, CO2, Cl, BUN, Cr, AST, ALT, AP, TB, TP, albumin, LDH, and uric acid should be performed at screening, pre-dose (within 4 hours prior to venetoclax administration), every 12 hours during venetoclax ramp-up period (see Appendix C for tumor lysis management guidelines), twice weekly otherwise during induction cycles and at the beginning of each maintenance cycle and relapse/EOT

f: CBC with differential. To be performed at screening, twice weekly during induction cycles, and at the beginning of each maintenance cycle and relapse/EOT.

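### Sections 6.4.1 and 6.4.1.1 conflict on whether a patient taking a strong CYP3A inhibitor may start and ramp up venetoclax

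*Combined protocol and SAP*

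**What the plan says.** Three parts of the protocol deal with CYP3A inhibitors while venetoclax is being started.

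- **Section 6.4.1** gives a general rule: "Concomitant use of venetoclax with strong inhibitors of CYP3A at initiation and during ramp-up phase is contraindicated". For patients who are past ramp-up and on a steady dose, it says to "reduce the dose by at least 75% when used concomitantly with strong CYP3A inhibitors". Moderate inhibitors are to be avoided; if one is unavoidable, the dose is cut by at least 50%.
- **Section 6.4.1.1** opens with "The dose of venetoclax should be adjusted to the following doses if taken with these antifungal medications" and then lists three schedules. The one headed "Strong CYP3A Inhibitors (ex. Voriconazole") and the one for posaconazole both begin "Ramp-up Day 1- 20 mg venetoclax", followed by 50 mg on ramp-up Day 2. The footnote to the venetoclax row of the regimen table in Section 6.1 points here.
- **Section 11, note V**, reads "Dosing ramp-up on days 1-3 or 1-4 (based on concurrent use of CYP3A inhibitors as outlined in Section 6.3.1").

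Two other places bear on the point. Section 9.3 says that "concurrent antifungal medications will be grouped as strong (e.g., posaconazole, voriconazole"), so the protocol itself treats posaconazole as strong. Section 2.5.4 says: "Antifungal agents, which are routinely administered concurrently with venetoclax, are moderate-to-strong inhibitors of CYP3A4".

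**The concern.** A general rule forbids a combination during a defined period, and the subsection beneath it gives doses for that combination in that period. A pharmacist who follows the footnote in Section 6.1 to 6.4.1.1 finds a Day 1 dose for a patient on voriconazole or posaconazole and can dispense it. A pharmacist who reads 6.4.1 finds that the same patient may not start. Nothing says that 6.4.1.1 is an exception, and the eligibility criteria in Sections 3.1 and 3.2 do not mention CYP3A inhibitors, so the question is not settled at entry.

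The conflict falls at a sensitive time. Section 6.4.2 treats every patient as at high risk of tumour lysis, requires urgent chemistry every 12 hours during ramp-up, and holds each further ramp-up dose until the 24-hour results have been reviewed. The DLT window in Section 6.3 opens only on Cycle 1 Day 15, so an event during ramp-up falls before the period that the dose-finding rules count. The written instruction on co-medication is therefore one of the safeguards at that point, and it contradicts itself.

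**Working it through.** The point is mainly textual. The arithmetic shows where the sections agree and where they do not.

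**Inputs.** Unadjusted ramp-up (Section 6.1): 100, 200 and 400 mg on Days 1, 2 and 3, identical at dose levels 1, -1 and -2, which differ in the number of venetoclax days. Adjusted doses: Section 6.4.1.1. Required reductions: Section 6.4.1.

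**Formula.** Reduction = 1 − adjusted dose / unadjusted dose.

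| Co-medication | Day 1 | Day 2 | Day 3 onward | Section 6.4.1 |
|---|---|---|---|---|
| Posaconazole (20/50/70 mg) | 1 − 20/100 = 80% | 1 − 50/200 = 75% | 1 − 70/400 = 82.5% | Not permitted in ramp-up; at least 75% afterwards |
| Strong inhibitor (20/50/100 mg) | 1 − 20/100 = 80% | 1 − 50/200 = 75% | 1 − 100/400 = 75% | Not permitted in ramp-up; at least 75% afterwards |
| Moderate inhibitor (50/100/200 mg) | 1 − 50/100 = 50% | 1 − 100/200 = 50% | 1 − 200/400 = 50% | At least 50% |

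**Reading the table.**

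1. Moderate inhibitors: 50% at every step meets the rule of at least 50%. No conflict.
2. Strong inhibitors and posaconazole from Day 3: 75% and 82.5% meet the rule of at least 75%. No conflict.
3. Strong inhibitors and posaconazole on Days 1 and 2: 6.4.1 permits no co-administration, while 6.4.1.1 gives 20 mg and then 50 mg. This is the conflict.

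**Calendar and cross-references.** Both tables in Section 6.1, and all three schedules in 6.4.1.1, reach their final dose on Day 3. No schedule has a fourth ramp-up day, so the longer option in note V has nothing behind it. Note V and Section 2.3.2 both refer to Section 6.3.1 for the adjustments, and Section 2.3.2 also to 6.3.1.1. Section 6.3.1 defines who is evaluable for toxicity, and there is no Section 6.3.1.1. The text meant is in 6.4.1 and 6.4.1.1.

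No sample size, error rate or power figure in Section 9 depends on any of this.

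**The case against.** The best defence is that 6.4.1.1 is conditional: its doses apply only if one of the listed drugs is taken. A site that never gives a strong inhibitor during ramp-up breaches neither section, nor the calendar, which offers alternatives. That stands against any claim that compliance with all three texts is impossible. It does not remove the conflict. On that reading the ramp-up doses for strong inhibitors and posaconazole would never be used, yet the regimen table directs sites to them and the calendar describes a ramp-up that varies with inhibitor use.

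It can also be said that tumour lysis risk is already heavily managed, by the measures in Section 6.4.2 and the white-cell limit of 25,000 on Day 1 in Section 3.1.12. That is fair and limits the likely harm, but it does not tell a site whether the patient may start.

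A reader might go further and infer any of the following. The documents do not support them.

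- **Patients at one dose level had incomparable exposure, which undermines the DLT decision.** The DLT window opens on Cycle 1 Day 15, and the sections agree from Day 3. Days 1 to 3 are the same at every dose level. The documents give no exposure figures, and the lower doses may be meant to offset the inhibitor.
- **The contradiction amounts to a 75% to 83% difference in dose.** Those percentages are the size of the planned adjustment. The Day 3 values among them lie where the sections agree.
- **Much of the cohort is affected.** Section 2.5.4 says antifungals are routine and range from moderate to strong inhibitors. It does not say how many patients take a strong one, or that they take it on Day 1.

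**Conclusion.** The contradiction is real and is resolved nowhere in the protocol. Its extent is narrow: whether a patient on a strong CYP3A inhibitor may start venetoclax, and the dosing on the first two days if so. A calendar note with an unsupported four-day ramp-up and wrong section references in two places add to it. It is a patient-safety inconsistency that should be corrected. It is not a flaw in the 3+3 rules or in the expansion-cohort test.

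The conclusion rests on two readings. First, posaconazole counts as strong, as Section 9.3 says; without that, the conflict remains for the strong-inhibitor schedule. Second, ramp-up means Days 1 and 2, as 6.4.1.1 labels them. Section 2.3.2 and the calendar count Day 3 within ramp-up; on that count the disagreement over permission would last one day longer, with the Day 3 reductions unchanged. The number of patients affected depends on the share taking a strong inhibitor at the start. The documents do not give that share, so no count is offered.

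**What to change.** Amend Sections 6.4.1 and 6.4.1.1 and note V of the Section 11 calendar so that all three give one consistent instruction on strong CYP3A inhibitors during ramp-up. Which instruction stands is the sponsor's clinical decision, and none is proposed here. This is not a request to merge the posaconazole schedule with the one for other strong inhibitors; their difference is not shown to be an error.

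In the same amendment, reconcile the four-day option in note V with the dosing schedules, and correct the references to Sections 6.3.1 and 6.3.1.1 in Section 2.3.2 and to Section 6.3.1 in note V.

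The cost is protocol wording only. No new data are needed: Section 6.4.1.1 already requires the case report form to record all concurrent drugs, and the calendar has them assessed at screening and at the start of each cycle. Sample size and analysis are unchanged.
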